#### Tipping Point Sensitivity Analysis: DBT Efficacy Analysis Set

A tipping point sensitivity analysis is performed for the DBT efficacy analysis set if the p-value  $\leq 0.05$  for the treatment group comparison for the main analysis of the overall DBT.

The analysis is performed using the following steps:

- 1) A shift parameter of  $\delta = 0$  is selected.
  - a) Data are imputed under the missing not at random (MNAR) assumption for the rimegepant treatment group with a shift adjustment and the missing at random (MAR) assumption for the placebo treatment group using SAS proc mi for  $n = 30$  data sets.
    - i) Subjects with <14 days of eDiary efficacy data in a specified month in the on-DBT efficacy analysis period have missing data imputed in that month.
    - ii) Data imputation is applied to each treatment group.
    - iii) The fully conditional specification (FCS) method is used with regression to impute data at Months 1 to 3.
    - iv) The imputation model specifies variables in the following order: changes from OP in the number of total migraine days per month at Months 1 to 3, age, sex, race, 4-level randomization stratum, and treatment group. Race may be reduced to fewer levels (e.g., white versus non-white) based on the availability of data.

- v) A shift of  $\delta$  is applied to imputed data only for subjects in the rimegepanti treatment group.
  - b) Each imputed data set in step 1a is analyzed using the same model from the main analysis (see Section 9.3.1).
  - c) Results from each model analysis in step 1b are combined to produce a pooled difference in LSM change, SE, 95% CI, and p-value using SAS proc mianalyze.
- 2) The p-value for the treatment group comparison of the overall DBT is compared to 0.05.
- a) If  $p\text{-value} \leq 0.05$ , then  $\delta$  is incremented by 0.1, and step 1 is repeated.
  - b) If  $p\text{-value} > 0.05$ , then the iterative process stops, and the last  $\delta$  used becomes the tipping point.

For each shift parameter, the same statistics are provided as those in the main analysis, but only for the overall DBT. Results across all shift parameters are displayed together in the same table.

### 6.3.2 Secondary Efficacy Endpoints

#### 6.3.2.1 Percentages of Subjects With Reductions From OP in Number of Migraine Days per Month Over Time on DBT

Analyses are based on the migraine analysis set with eDiary efficacy data dates in the OP and on-DBT efficacy analysis periods (see Section 7.2).

In analyses by months, subjects must (1) achieve the reduction criterion from OP in the number of migraine days per month in the specified month, (2) have  $\geq 14$  days of eDiary efficacy data (not necessarily consecutive) in the specified month, and (3) have  $\geq 1$  migraine day (absolute not prorated) of appropriate pain intensity in the OP analysis period to be classified as responders in the specified month. Otherwise, subjects are classified as failures in the specified month.

In analyses of the overall DBT, subjects must (1) achieve the reduction criterion from OP in the number of migraine days in the overall DBT, and (2) have  $\geq 1$  migraine day (absolute not prorated) of appropriate pain intensity in the OP analysis period to be classified as responders. Otherwise, subjects are classified as failures.

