9.1. Sample Size

The study will randomize approximately 300 subjects per treatment group. Based on data from study BHV3000-305 and subgroup analysis from the galcanezumab Phase 3 program,^{6,9,10} we estimate that rimegepant will provide roughly a 1.0-day advantage over placebo on the primary endpoint, and assuming a common standard deviation of 3.6 days. Assuming that roughly 280 subjects per treatment group will contribute to the final migraine analysis dataset, the study will have roughly 90% power on the primary endpoint at a 2-sided alpha level of 0.05.

In study BHV3000-305, rimegepant dosed EOD provided a 1.0-day advantage over placebo dosed EOD in subjects who were not taking prophylactic migraine medication through randomization. Using the data from study BHV3000-305, the standard deviation of the primary endpoint was estimated to be roughly 3.6 days for these subjects.

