9.3.1.2. Secondary Endpoints

The proportion of subjects with $\geq 50\%$ reduction from the Observation Phase in the number of migraine days of moderate or severe headache pain intensity per month over the entire DBT Phase (Weeks 1 to 12) will be assessed using Mantel-Haenszel risk estimation with stratification by randomization stratum for the DBT migraine analysis set. Missing data are imputed as non-response (i.e., failure). The difference estimate (rimegepant – placebo), SE, p-value, and 95% CI will be reported.

The mean change from the Observation Phase in the number of migraine days per month in the first 4 weeks (Weeks 1 to 4) of the DBT Phase will be assessed for the DBT migraine analysis set from the same model used for the primary endpoint.

The mean change from the Observation Phase in the number of migraine days per month in the last 4 weeks (Weeks 9 to 12) of the DBT Phase will be assessed for the DBT migraine analysis set from the same model used for the primary endpoint.

The mean changes from baseline in MSQ restrictive role function domain score and MIBS score at Week 12 will be assessed for the DBT efficacy analysis set using a linear mixed effects model with repeated measures that will include the following variables: change from baseline in the score as the dependent variable; baseline score as a covariate; and fixed effects for treatment group, randomization stratum, week, and week-by-treatment group interaction. Weeks are 4, 8, and 12. The Week 12 difference estimate (rimegepant – placebo),

SE, 95% CI, and p-value will be reported for each endpoint. The Huber-White "sandwich" estimator will be used for the estimation of SEs.

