## **Intercurrent Events**

Intercurrent events are those that occur after treatment initiation and either preclude observation of the endpoint or affect its interpretation.

Study drug discontinuation before the time point of interest defining the endpoint is considered an intercurrent event.

- For efficacy objectives assessed with a continuous endpoint, study drug discontinuation is handled with a “hypothetical strategy,” i.e., the hypothetical scenario is that had subjects not discontinued study drug, their efficacy would have been similar to the efficacy of subjects from the same treatment group and randomization stratum who did not discontinue study drug. All observed values of the endpoint of interest are excluded after study drug discontinuation plus 1 day (see Section 7.2), and statistical methods are used to estimate the treatment effect that would have been seen had the intercurrent event not occurred.
- For efficacy objectives assessed with a binary or time-to-event endpoint, study drug discontinuation is handled with a “composite strategy,” i.e., the occurrence of the intercurrent event is integrated as a component of the endpoint. All observed values of the endpoint of interest are excluded after study drug discontinuation plus 1 day (see Section 7.2). Subjects with missing data are considered failures for binary endpoints. Subjects who achieve the response criteria before study drug discontinuation are considered to have an event for time-to-event endpoints.
- For safety objectives, study drug discontinuation is handled with a “while-on-treatment strategy,” i.e., response to treatment prior to the occurrence of the intercurrent event of interest, such that all observed values of the endpoint of interest are used prior to study drug discontinuation plus 7 days (see Section 7.2 and the Core SAP).
- For outcomes research objectives, study drug discontinuation is handled with a “treatment policy strategy,” i.e., the occurrence of the intercurrent event is considered irrelevant, such that all observed values of the endpoint of interest are used regardless of study drug discontinuation.

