**Table 2 Key Secondary Objective Estimands**

Objective 1	Proportion of subjects with <math>\geq 50\%</math> reduction from the OP in the number of moderate or severe migraine days per month over the entire DBT Phase
Efficacy Endpoint	Proportion of subjects with $\geq 50\%$ reduction from the OP in number of moderate or severe migraine days per month over the entire DBT Phase (Weeks 1 to 12)
Summary	Percentage of subjects by treatment group, and difference in percentages between treatment groups using Mantel-Haenszel risk estimation for the migraine analysis set
Intercurrent Events	Study drug discontinuation: composite strategy Nonstudy prophylactic migraine medication use: treatment policy strategy Nonstudy acute migraine-specific medication use: composite strategy Use of nonstudy other medication to treat headache (migraine or nonmigraine) or aura: treatment policy strategy
Objective 2	Mean reduction from the OP in the number of migraine days per month in the first 4 weeks of the DBT Phase
Efficacy Endpoint	Mean change from the OP in the number of migraine days per month in the first 4 weeks (Weeks 1 to 4) of the DBT Phase
Summary	Mean change from the OP by treatment group using descriptive statistics and linear mixed effects model with repeated measures, and difference in mean changes between treatment groups from model for the migraine analysis set
Intercurrent Events	Study drug discontinuation: hypothetical strategy Nonstudy prophylactic migraine medication use: treatment policy strategy Nonstudy acute migraine-specific medication use: composite strategy

	Use of nonstudy other medication to treat headache (migraine or nonmigraine) or aura: treatment policy strategy
Objective 3	Mean reduction from the OP in the number of migraine days per month in the last 4 weeks of the DBT Phase
Efficacy Endpoint	Mean change from the OP in the number of migraine days per month in the last 4 weeks (Weeks 9 to 12) of the DBT Phase
Summary	Mean change from the OP by treatment group using descriptive statistics and linear mixed effects model with repeated measures, and difference in mean changes between treatment groups from model for the migraine analysis set

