### Treatment Group Comparisons

For each pain intensity (total; moderate or severe) and select percentage reduction ( $\geq 30\%$ ,  $\geq 50\%$ ,  $\geq 75\%$ , and  $100\%$ ), the percentages of subjects with reductions from the OP in the number of migraine days per month are compared between rimegepant and placebo using Mantel-Haenszel risk estimation (e.g., SAS proc strdate) with stratification by 4-level randomization stratum. Percentages are calculated against the number of subjects in the migraine analysis set at all time points.

The table displays the following statistics at each month of the DBT Phase and overall DBT by headache pain intensity:

- Response rate (i.e., “n/N” and percentage), ASE, and 95% CI for each treatment group
- Stratified percentage difference between rimegepant and placebo (rimegepant – placebo), ASE, 95% CI, and p-value.

Results for the endpoint of  $\geq 50\%$  reduction of moderate or severe pain intensity in the overall DBT support key secondary objective #1. Results for all other endpoints support exploratory objective #2.

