### Results support exploratory objective #5.

#### **6.3.3.6      *Time to Percentage Reduction From OP in Number of Migraine Days and Number of Headache Days per Month Over Time on DBT***

The following time-to-event endpoints are assessed by headache pain intensity (total; moderate or severe) for the migraine analysis set:

- 1) Time to  $\geq 30\%$  reduction from the OP in the number of migraine days per month
- 2) Time to  $\geq 50\%$  reduction from the OP in the number of migraine days per month.

Each time-to-event endpoint is assessed by headache pain intensity using a time-to-event distribution summary table presenting the following statistics: number and percentage of subjects with events; number and percentage of subjects censored; time to event median with 95% CI and quartiles, where the 95% CI for the median is estimated using the method of Brookmeyer and Crowley.

Each time-to-event endpoint is also assessed using a Cox proportional hazards model with the following variables: age, sex, race, 4-level randomization stratum, and treatment group. Race may be reduced to fewer levels (e.g., white versus non-white) based on the availability of data. The hazard ratio estimate (rimegepant versus placebo), 95% CI, and p-value are reported.

For a given time-to-event endpoint, subjects are considered to have an event through Month 3 based on the first month that they are evaluable and the endpoint is achieved. Otherwise, subjects

who do not have an event through Month 3 are censored at the last month they are evaluable. Subjects must have  $\geq 14$  days of eDiary efficacy data (not necessarily consecutive) in a month to be evaluable at that month.

All analyses described above are performed analogously for headache days per month.

Results support exploratory objective #6.

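### For the first key secondary endpoint, the overall-DBT responder rule lets early discontinuers count as Weeks 1 to 12 responders, contrary to the stated composite strategy.

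*SAP*

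**What the plan says.** **The strategy.** SAP 3.2 (Intercurrent Events) handles study drug discontinuation for binary efficacy endpoints with a composite strategy, meaning that the event becomes part of the endpoint. Values later than one day after discontinuation are excluded, and "Subjects with missing data are considered failures for binary endpoints". SAP Table 2, Objective 1, applies this to key secondary 1: "Study drug discontinuation: composite strategy". Protocol 9.3.1.2 likewise treats missing data as non-response for this endpoint, in the DBT migraine analysis set.

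**The rule.** SAP 6.3.2.1 has two responder definitions. The by-month definition requires at least 14 diary days in the month concerned. The overall definition, which serves key secondary 1, reads "In analyses of the overall DBT, subjects must (1) achieve the reduction criterion from OP in the number of migraine days" over the whole DBT Phase, plus at least one Observation Phase (OP) migraine day of the relevant intensity. It has no condition on discontinuation, completion or amount of diary data.

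**The value and the denominator.** SAP 6.3.1 computes the overall value as 28 × migraine days ÷ diary days available through Month 3. SAP 7.2 ends the on-DBT period no later than one day after the last double-blind dose. For the denominator: "Percentages are calculated against the number of subjects in the migraine analysis set at all time points". SAP 4.1 admits subjects to that set if they have at least 14 diary days in the OP and in at least one DBT month.

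**The concern.** The strategy and the rule do not describe the same quantity. Under the strategy, stopping double-blind drug should prevent a subject from being a responder over Weeks 1 to 12. Under the rule, stopping has no consequence: later days are removed, the remaining days are scaled to 28, and the subject is judged on those. That is close to a while-on-treatment response, not a composite one.

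Key secondary 1 is tested at two-sided 0.05 directly after the primary endpoint, and key secondaries 2 to 5 can be claimed only if it succeeds (SAP 5). The jump-to-reference and tipping-point analyses in SAP 6.3.1.3 cover only the primary endpoint, so no planned sensitivity analysis addresses how discontinuers are handled here.

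**Working it through.** **The plan's own figure.** The only power statement concerns the primary endpoint: "the study will have roughly 90% power on the primary endpoint at a 2-sided alpha level of 0.05". Its inputs are a 1.0-day difference, SD 3.6 and 280 per arm (Protocol 9.1). The standard error is 3.6 × √(2/280) = 0.304; 1.0/0.304 = 3.29; 3.29 − 1.96 = 1.33; power = 0.908. The figure reproduces. No response rate or power is stated for key secondary 1.

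**Can the overall value be missing?** Every subject in the migraine set has at least 14 on-DBT diary days in some month, so the divisor is at least 14 and the value always exists. The missing-equals-failure rule therefore has nothing to act on within this set.

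**A worked case.** Take a subject with 8 moderate or severe migraine days per 28 in the OP and a last double-blind dose on Day 13.
- On-DBT data run to Day 14, giving up to 14 diary days, so the subject is in the migraine set.
- With 2 such days in 14, the prorated value is 28 × 2/14 = 4.0.
- The reduction is 1 − 4.0/8 = 50%, so the subject is an overall responder with 14 of 84 days observed.
- Under the by-month definition in the same section, the subject fails Months 2 and 3.

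**Short observation makes chance response easier.** The table gives the binomial probability of a prorated reduction of at least 50% when nothing has truly changed, at a true rate of 8 days per 28:

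| OP count | 14 diary days | 84 diary days |
|---|---|---|
| Fixed at the true rate | 19.0% | 0.2% |
| Also random | 14.9% | 1.6% |

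**Possible size (illustration only).** The documents supply 300 randomised and about 280 in the migraine set per arm. These rates are assumptions: completers respond at 45% (rimegepant) and 35% (placebo); late discontinuers in the migraine set meet the prorated criterion at 40% and 30%; late discontinuation is 13% (39 of 300) or 8% (24 of 300). The denominator stays at 280.

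- As written: (completers × completer rate + discontinuers × discontinuer rate)/280. For rimegepant at 13%: (241 × 0.45 + 39 × 0.40)/280 = 44.3%.
- Discontinuation as failure: completers × completer rate/280. For rimegepant at 13%: 241 × 0.45/280 = 38.7%.

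| Late discontinuation, rimegepant / placebo | As written | Discontinuation = failure |
|---|---|---|
| 13% / 13% | 44.3% − 34.3% = 10.0 points | 38.7% − 30.1% = 8.6 points |
| 13% / 8% | 44.3% − 34.6% = 9.7 points | 38.7% − 32.0% = 6.7 points |
| 8% / 13% | 44.6% − 34.3% = 10.3 points | 41.1% − 30.1% = 11.0 points |

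With late discontinuation proportions d, the change in the difference is −(0.40 × d on rimegepant − 0.30 × d on placebo) × 300/280. Under these rates the difference widens once placebo discontinuation exceeds 4/3 of rimegepant discontinuation.

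**The case against.** **Missing could mean a wholly missing endpoint.** The rule would then be formally obeyed. But proration leaves it empty for this endpoint, and discontinuation is still not a component of the outcome, which is what the composite label promises.

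**The by-month results give some protection.** The same table reports Month 3 response against the full migraine set, and most earlier discontinuers fail there. That is prespecified and useful, but it supports an exploratory objective and is outside the hierarchy. It is also imperfect: a last dose on Day 69 still leaves 14 Month 3 diary days (57 to 70).

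**A reader might infer that the denominator is also an error**, because subjects who stop by Day 12 have at most 13 diary days and drop out of the set instead of failing. The documents do not support this. Table 2 names the migraine set beside the composite strategy, and Protocol 9.3.1.2 names it immediately before its missing-data rule. Both apply the failure rule within that set. Nor are the roughly 20 per arm outside it all early dropouts: SAP 6.3 also lists untreated subjects, subjects randomised more than once, and subjects with too few OP diary days.

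**A reader might also infer that the exploratory time-to-event endpoint shares the defect**, since subjects "who do not have an event through Month 3 are censored at the last month they are evaluable" while the strategy is labelled composite. SAP 3.2 defines the handling for those endpoints separately: response before discontinuation counts as an event. It does not say that non-responding discontinuers remain at risk. SAP 6.3.3.6 follows that definition.

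**Conclusion.** The inconsistency is real and confined to one place: the overall-DBT responder rule in SAP 6.3.2.1, with the prorated value from 6.3.1, does not carry out the composite strategy stated for key secondary 1. This follows from the text and depends on no assumed rate. It needs correcting because the endpoint is alpha-controlled and gates four others.

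Its numerical effect is unknown. The documents give no responder rates and no DBT discontinuation rate; the roughly 480 of 600 expected to enter the extension is not a discontinuation rate. A reader might conclude that the rule favours rimegepant. That would require an assumption about which arm loses more subjects, and nothing in the documents supports one. Relative to the stated composite, the illustrative difference falls by 1.4 points with equal 13% discontinuation, falls by 3.0 with 13% on rimegepant against 8% on placebo, and rises by about 0.7 when those are reversed.

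**What to change.** In SAP 6.3.2.1, add to the overall-DBT rule that a subject who discontinues double-blind study drug before completing the DBT Phase is a failure. Identify these subjects from the DB Subject Status CRF and the DB study drug last date, which SAP 6.2.3.3 already uses for disposition, and state which source governs when the two disagree. Keep the current prorated version as a sensitivity analysis. As a supplementary sensitivity analysis, repeat the endpoint in the DBT efficacy analysis set with non-evaluable subjects counted as failures.

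Do not simply extend the requirement of 14 diary days to every month. That measures diary completeness, not discontinuation: it would pass a subject whose last dose is on Day 69 and fail a completer with one sparse month.

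In the same edit, correct SAP 6.3.2.3, which places this endpoint in the last month of the DBT Phase, whereas Table 2 and Protocol 3.2.1 define it over Weeks 1 to 12.

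The cost is SAP wording and a small programming change, to be made before unblinding at the PCD database lock. The primary denominator does not change. Response rates will fall somewhat in both arms.

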### Treatment Group Comparisons

For each pain intensity (total; moderate or severe) and select percentage reduction ( $\geq 30\%$ ,  $\geq 50\%$ ,  $\geq 75\%$ , and  $100\%$ ), the percentages of subjects with reductions from the OP in the number of migraine days per month are compared between rimegepant and placebo using Mantel-Haenszel risk estimation (e.g., SAS proc strdate) with stratification by 4-level randomization stratum. Percentages are calculated against the number of subjects in the migraine analysis set at all time points.

The table displays the following statistics at each month of the DBT Phase and overall DBT by headache pain intensity:

- Response rate (i.e., “n/N” and percentage), ASE, and 95% CI for each treatment group
- Stratified percentage difference between rimegepant and placebo (rimegepant – placebo), ASE, 95% CI, and p-value.

Results for the endpoint of  $\geq 50\%$  reduction of moderate or severe pain intensity in the overall DBT support key secondary objective #1. Results for all other endpoints support exploratory objective #2.

### 6.3.2.2 *Acute Migraine-Specific Medication Days per Month Over Time on DBT*

Acute migraine-specific medication days per month are assessed as “acute migraine-specific medication days per 4 weeks” to correspond with the 4-week visit schedule. Acute migraine-specific medication days per month are based on 4-week intervals, and are prorated to account for missing migraine reports. See Section 9.2.4 for the definition of acute migraine-specific medication days.

Analyses are based on the migraine analysis set with eDiary efficacy data dates in the on-DBT efficacy analysis period.

The number of acute migraine-specific medication days per month in the DBT Phase are prorated to 28 days and derived as follows:

- Month (i.e., 4-week interval) in the on-DBT efficacy analysis period:  $28 \times (\text{total number of acute migraine-specific medication days in the month}) / (\text{total number of eDiary efficacy data days in the month})$ . Subjects must have  $\geq 14$  days of eDiary efficacy data (not necessarily consecutive) in the specified month to be evaluable.
- Overall DBT:  $28 \times (\text{total number of acute migraine-specific medication days through Month 3 in the on-DBT efficacy analysis period}) / (\text{total number of eDiary efficacy data days through Month 3 in the on-DBT efficacy analysis period})$ .

